## **5.4. Blinding**

This is an open-label trial; blinding procedures are not applicable.

## 5.5. Treatment Compliance

Clinical personnel at the site will record in the source notes the timing and site of all administrations of IMP. Any reasons for non-compliance should be documented.

Drug accountability on a patient level will be documented by keeping copies of the IMP order form and the IMP administration form and the completed appendices to the IMP manual. The documentation will be reviewed periodically and verified by the Trial Monitor over the course of the trial.

### 5.5.1. Overdose, Medication Errors, and Misuse

An overdose is defined as a patient receiving a dose of the IMP in excess of that specified in this protocol.

Medication errors and uses outside what is foreseen in the protocol, including misuse of the product, may include:

- Administration of wrong drug
- Wrong route of administration, such as IV instead of intracerebroventricular
- Administration of an overdose with the intention to cause harm, or misuse of trial treatment
- Accidental administration of a lower or higher dose than intended. The administered dose must deviate from the intended dose to an extent where clinical consequences for the trial patient were likely to happen as judged by the investigator, although the clinical consequences did not necessarily occur.

Overdose/underdose and medication errors (exceeding  $\pm 10\%$  as compared to protocol-specified dose) should be reported in the electronic case report form (eCRF), including information on the quantity of the excess dose as well as the duration (if an overdose) and of the type (if a medication error).

If an overdose, medication error, or misuse result in an AE this should be reported as an AE in the eCRF and (if serious) to [[contact]](mailto:[contact]) using the clinical AE report form.

#### 5.5.1.1. *Management of Overdose of Lu-DTPA-omburtamab*

Rescue medication to reverse the action of Lu-DTPA-omburtamab is not available. In case of overdose or other medication errors of Lu-DTPA-omburtamab patients, should receive supportive care according to local guidelines and potential side effects of Lu-DTPA-omburtamab should be treated systematically.

In the event of an overdose, the Investigator should:

- Contact Medical Monitor (for contact details, see the [protocol front page](#))
- Closely monitor the patient for any AE and laboratory abnormalities
- In case of an AE, close medical supervision and monitoring should continue until the patient recovers.

## **5.6. Technical complaint**

A technical complaint is any written or oral communication that states any dissatisfaction with the product characteristics and alleges a product defect. A complaint can be related to e.g., the product appearance (discoloration, presence of particles, or sediment), product container (damaged or missing seal), product label (damaged, missing, misleading), or consignment (wrong number of vials in the package). Complaint should also be initiated if the product is suspected to be falsified.

Please refer to the IMP manual for information regarding reporting of a technical complaint.

## 6. CONCOMITANT THERAPIES

Any medication or vaccine (including over-the-counter or prescription medicines, vitamins, and/or herbal supplements) that the patient is receiving at the time of enrolment or receives during the trial must be entered on the eCRF, including:

- reason for use
- dates of administration, including start and end dates, and
- dosage information including dose and frequency.

Prior anti-cancer therapy must be entered in the eCRF. The Medical Monitor should be contacted if there are any questions regarding concomitant or prior therapy.

### 6.1. Permitted Concomitant Therapy

Any treatment needed for patient wellbeing (including supportive care) that will not interfere with IMP administration may be given at the discretion of the investigator. Additional anti-cancer and supportive care treatments are allowed after the EOT Visit. If an MRI is scheduled at that visit, the MRI should be completed before starting the additional treatments. Medical marijuana is permitted if the patient was receiving this therapy prior to signing the ICF.

After discontinuation of the IMP, any treatment deemed safe and justified by the investigator can be administered according to clinical practice and at the discretion of the investigator.

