#### **4.2. Exclusion Criteria**

Patients will be excluded from the trial if they satisfy any of the following criteria at the Screening Visit unless otherwise stated:

1. Obstructive or symptomatic communicating hydrocephalus as determined by Ommaya patency/CSF flow assessment.
2. Any tumor lesion measuring  $>15$  mm in the smallest diameter.
3. Ventriculoperitoneal (VP) shunts without programmable valves. Ventriculo-atrial or ventriculo-pleural shunts.
4. Grade 4 nervous system disorder. Stable neurological deficits due to brain tumor or surgery and hearing loss are allowed.
5. Uncontrolled life-threatening infection.
6. Received radiation therapy (focal or crano-spinal irradiation), systemic or intrathecal cytotoxic chemotherapy, or immunotherapy (including monoclonal antibodies; corticosteroids not included) less than 3 weeks prior to the Dosimetry Dose (or until recovery from clinically significant adverse events). Received nitrosoureas less than 6 weeks prior to the Dosimetry Dose.
7. Received any prior anti-B7-H3 treatment.
8. Non-hematologic organ toxicity Grade 3 or above; specifically, any renal, cardiac, hepatic, pulmonary, and gastrointestinal system toxicity.
9. Other significant disease or condition that in the investigator's opinion would exclude the patient from the trial.

10. Females of childbearing potential (as defined in [Appendix 5](#)) who are pregnant, breast feeding, intend to become pregnant, or are not using highly effective contraceptive methods as defined in [Appendix 5](#) or males who are not using highly effective contraceptive methods as defined in [Appendix 5](#).

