##### **4.3.2. End of Treatment**

The end of treatment (EOT) is defined as the day the last dose of Lu-DTPA-omburtamab is received. The EOT Visit should occur 5 to 6 weeks after the last dose, whether this is a premature treatment discontinuation or treatment completion.

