### 6.2. Prohibited Concomitant Therapy

The following therapies are prohibited within 3 weeks prior to the first dose and until completion of the EOT Visit:

- Additional cytotoxic anti-cancer therapy.
- Any other IMP.
- Any live viral vaccines.
- Herbal medications with known risk of hepatotoxicity.

The following is prohibited in Part 1 Cycle 1 within 1 week prior to first IMP administration and until 5 weeks after:

- Additional hematological support.

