#### Non-serious Events:

Non-serious AEs should be reported from the day of first IMP administration until 5 weeks after the patient's last dose. Thereafter and during the follow-up and post-trial monitoring periods, new onset of cancers regardless of causality, should be reported, until death or at least 10 years after end of trial, whichever comes first. During the follow-up period, Grade 3 or higher non-serious AEs considered related to IMP or related to the presence of the indwelling catheter system should be reported. Non-serious AEs occurring between signing the ICF and the first IMP administration must be recorded as medical history.

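### Sections 6.1 and 6.2 disagree on when other anti-cancer therapy may start after the study drug is stopped, and neither the DLT evaluable set nor the TEAE tables say how to handle patients who start it

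*Combined protocol and SAP*

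**What the plan says.** Section 6.1 makes two statements. The first: "Additional anti-cancer and supportive care treatments are allowed after the EOT Visit". The second, in its closing paragraph and not tied to any visit: "After discontinuation of the IMP, any treatment deemed safe and justified by the investigator can be administered".

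Section 6.2 opens its list with "The following therapies are prohibited within 3 weeks prior to the first dose and until completion of the EOT Visit". The anti-cancer entry on that list is "Additional cytotoxic anti-cancer therapy"; other investigational products are a separate entry. Exclusion criterion 6 in Section 4.2 is wider and names the classes one by one: "Received radiation therapy (focal or crano-spinal irradiation), systemic or intrathecal cytotoxic chemotherapy, or immunotherapy". It applies only before dosing.

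On the timing of the visit, Section 4.3.2 says: "The EOT Visit should occur 5 to 6 weeks after the last dose, whether this is a premature treatment discontinuation or treatment completion". Section 4.3.5 asks discontinued patients to attend as soon as possible. In Appendix 3, note 2 to Table 6 puts the EOT Visit in place of the Day 29 visit when treatment stops after Cycle 1.

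On the endpoints, Section 2.2.1 makes the number of DLTs primary in Part 1 and the number and severity of TEAEs primary in Part 2. Section 3.1.1.2 counts DLTs over 5 weeks from the first administration in Cycle 1, which is the dosimetry dose. Under Section 7.4.5, "Non-serious AEs should be reported from the day of first IMP administration until 5 weeks" after the last dose; SAEs of any cause are collected to the same point. Section 8.5.2 treats any AE after first administration as treatment-emergent. Neither that definition nor the DLT Evaluable Analysis Set in Section 8.2 mentions new anti-cancer therapy.

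**The concern.** Early stopping is foreseeable in recurrent or refractory disease. Section 4.3.2.1 requires permanent discontinuation on progression before Cycle 2 in Part 1 or before Cycle 5 in Part 2. Two sites with the same patient could then act in opposite ways, and each could cite the protocol.

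In Part 1 this matters because a 3+3 decision rests on three to six patients. If other therapy starts inside the DLT window, later observation no longer reflects the study drug alone, and the error can go either way. Toxicity of the new therapy may be counted as a DLT, or a true DLT may be put down to the new therapy and missed. In Part 2, toxicity of later therapy enters the primary endpoint directly, since a TEAE needs no causal link to the study drug.

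**Working it through.** **1. How long the two sections disagree.** Take a Part 1 patient who has the dosimetry dose on Day 1 and the treatment dose on Day 8, and then stops. The DLT window ends at Day 1 + 35 = Day 36. Collection of all AEs ends at Day 8 + 35 = Day 43.

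| Source | EOT Visit | Relative to Day 36 |
|---|---|---|
| Section 4.3.2 | Day 8 + 35 = 43 to Day 8 + 42 = 50 | 7 to 14 days after |
| Table 6, note 2 | Day 29 (±1) | about 7 days before |
| Section 4.3.5 | as soon as possible, no day given | before or after |

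Under Section 4.3.2 the whole DLT window precedes the EOT Visit, so the disagreement between 6.1 and 6.2 can cover any part of the window left after the patient stops. Under Table 6 the visit falls at about Day 29. Even a site that follows 6.2 strictly could then start other therapy with about 36 − 29 = 7 days of the DLT window and 43 − 29 = 14 days of full AE collection remaining. Reconciling 6.1 with 6.2 is therefore not sufficient by itself; the analysis sets also need a rule.

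**2. Which therapies are covered.** Section 6.2 names cytotoxic therapy only. Exclusion criterion 6 lists radiation, cytotoxic chemotherapy and immunotherapy as separate items, so it is doubtful that cytotoxic in 6.2 was meant to include the other two. The first statement in 6.1 covers all anti-cancer treatment. The documents thus describe three different scopes.

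**3. Effect on a 3+3 decision.** Under Section 3.1.1.1, one DLT in the first three patients turns 0/3 (escalate) into 1/3 (enrol three more, if the DMC recommends it). One further DLT turns 1/6 (escalate) into 2/6 (stop). With DLT probability p per patient, the chance of escalating past a level is

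(1 − p)³ + 3p(1 − p)⁵.

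If a fraction c of patients had another therapy's toxicity counted as a DLT, p becomes p′ = 1 − (1 − p)(1 − c). The values of p and c below are assumptions for illustration; the documents give neither.

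| True p | c = 0 | c = 2% | c = 5% | c = 10% |
|---|---|---|---|---|
| 10% | 90.6% | 87.5% | 82.4% | 73.0% |
| 20% | 70.9% | 67.4% | 62.2% | 53.6% |

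For example, p = 10% and c = 5% give p′ = 1 − 0.90 × 0.95 = 0.145, and a chance of escalation of 82.4%. The table covers false DLTs only. Missed DLTs would push the other way.

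**4. Effect on the Part 2 endpoint.** The plan's sizing figure reproduces: 1 − 0.9²⁴ = 0.920, against the stated probability of at least 90% of detecting an AE of 10% incidence with 24 patients. The present point does not change it. Each patient whose event is due to later therapy adds 1/24 = 4.2 percentage points to that event's incidence.

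**The case against.** The case on the other side is substantial, and several parts of it stand.

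- **Duration.** A reader might take the conflict to last 5 to 6 weeks for every early stopper. That rests on Section 4.3.2 alone. Section 4.3.5 and Table 6 point to an earlier visit, and note 2 to Table 8 also allows for EOT Visits before the end of a Part 2 cycle.
- **Scope.** A reader might infer from 6.2 that radiotherapy, immunotherapy or targeted agents are freely permitted during treatment. The first statement in 6.1 implies that every anti-cancer class waits for the EOT Visit, so the fair description is inconsistent scope. The documents describe no targeted treatment for any molecular subgroup, so nothing can be built on that.
- **DLT attribution.** A reader might infer that toxicity of other therapy will simply be counted as a DLT. A DLT must be judged possibly or probably related, Section 7.4.5 classes events readily explained by other therapy as not related, and Section 3.1.1.1 gives the DMC the final assessment. Section 4.3.4 allows replacement of patients discontinued in the DLT period for reasons unrelated to the study drug.
- **TEAE reporting.** Section 8.5.2 summarises TEAEs by relationship and tabulates adverse drug reactions separately. Counting all TEAEs whatever their cause is a legitimate choice, and moving later events out of the main table could hide delayed myelosuppression.

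These safeguards are partial. Myelosuppression is the main toxicity reported for the iodine-131 product (Section 1.2.1) and is also plausible with chemotherapy or radiation, so such an event may not be readily explained by one cause. The relatedness filter can also discard a true DLT. Replacement is discretionary and is not triggered by new therapy. None of these safeguards defines a TEAE cut-off.

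**Conclusion.** The point holds in a limited form. The conflict between the closing paragraph of 6.1 and both its own first statement and 6.2 is on the face of the text. Its duration and the classes of therapy covered are unclear because other sections differ. As written, a Part 1 patient who stops early can start other anti-cancer therapy inside the 5-week window and remain DLT-evaluable, as DLT-free or with a confounded event. In Part 2, toxicity of later therapy counts in the primary endpoint without a cut-off, at 4.2 percentage points per affected patient.

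The documents do not support a claim that either primary endpoint is unprotected, or any estimate of how often this will occur. The escalation probabilities above depend wholly on assumed rates. The change is worth making because a single patient can alter a 3+3 decision and the remedy is mostly wording.

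**What to change.** 1. Reconcile Section 4.2 (criterion 6), Sections 4.3.2, 4.3.5, 6.1 and 6.2, and note 2 to Table 6 into one statement of which therapy classes are covered and until when, with one definition of EOT Visit timing. The clinical content is for the sponsor to decide.
2. Amend the DLT Evaluable Analysis Set in Section 8.2. A Part 1 patient who starts non-protocol anti-cancer therapy before the end of the DLT window, with no DLT before that start, is not DLT-evaluable and is handled under Section 4.3.4. Later events are still reported to the DMC and listed. Because the rule looks only at what happened before the new therapy, it does not keep confounded events while dropping DLT-free patients.
3. Keep all TEAEs as the main Part 2 table. Add a supplementary table of TEAEs with onset before the first non-protocol anti-cancer therapy.

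The cost is protocol and analysis wording, an occasional Part 1 replacement and one extra table. The sponsor should also confirm that on-study radiotherapy dates are captured: Section 6 requires dates for medications and vaccines but does not expressly mention radiotherapy given during the trial.

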### 6.2. Prohibited Concomitant Therapy

The following therapies are prohibited within 3 weeks prior to the first dose and until completion of the EOT Visit:

- Additional cytotoxic anti-cancer therapy.
- Any other IMP.
- Any live viral vaccines.
- Herbal medications with known risk of hepatotoxicity.

The following is prohibited in Part 1 Cycle 1 within 1 week prior to first IMP administration and until 5 weeks after:

- Additional hematological support.

## 6.3. Treatment of Expected Toxicities

### Premedication

Starting 24 hours prior to each Lu-DTPA-omburtamab infusion, dexamethasone will be administered orally at 0.6 mg/kg/day or an IV equivalent (subject to a maximum total dose of 20 mg/day) divided into twice-daily doses for a total of 3 days to alleviate infusion-related AEs.

An anti-pyretic (e.g., oral acetaminophen/paracetamol [15 mg/kg, 650 mg maximum]) and an antihistamine (e.g., diphenhydramine [1 mg/kg, 50 mg maximum]) or equivalents will be administered within 1 to 2 hours before all intracerebroventricular infusions.

### Expected Toxicities

Expected toxicities will be treated at the discretion of the investigator and could include the following:

- Urticaria will be treated with antihistamines.
- Fever will be treated with paracetamol/acetaminophen.
- During administration of Lu-DTPA-omburtamab, emergency support for anaphylaxis must be readily available, including epinephrine, diphenhydramine, hydrocortisone, and/or dexamethasone at the bedside.
- Patients with myelosuppression may be supported with blood products, GM-CSF, or granulocyte–colony-stimulating factor according to local standard of care. If indicated, patients also may have banked stem cells reinfused.

## 7. TRIAL ASSESSMENTS AND PROCEDURES

Trial procedures and their timing are summarized in the Schedule of Assessments ([Appendix 3](#)). As protocol waivers or exemptions are not allowed, with the exception of immediate safety concerns, these should be discussed with the sponsor immediately upon occurrence or awareness to determine if the patient should continue or discontinue the IMP. Adherence to the trial design requirements, including those specified in the Schedule of Assessments, is essential and required for trial conduct.

All screening evaluations must be completed and reviewed to confirm that potential patients meet all eligibility criteria. The investigator will maintain a screening log to record details of all patients screened and to confirm eligibility or record reasons for screening failure ([Section 4.3.1](#)), as applicable. Procedures conducted as part of the patient's routine clinical management (e.g., blood count) and obtained before signing the ICF may be utilized for screening or baseline purposes provided the procedure met the protocol-specified criteria and was performed within the timeframe defined in the Schedule of Assessments ([Appendix 3](#)).

The maximum amount of blood collected from each dosed patient over the duration of the trial, including any extra assessments that may be required, will not exceed 300 mL, and the maximum amount of CSF collected from each dosed patient over the duration of the trial, including any extra assessments that may be required, will not exceed 20 mL. In case the patient will participate in the ctDNA analysis, additional 3-5 ml CSF will be collected. Repeat or unscheduled samples may be taken for safety reasons or for technical issues with the samples.

### 7.1. Vital Signs, Physical Examination, and Other Safety Evaluations

#### 7.1.1. Demographics

The following demographic information will be entered in the eCRF during screening:

- Age or date of birth, if allowed by local legislation
- Gender
- Ethnic origin and race, if allowed by local legislation

#### 7.1.2. Height and Body Weight

Height (without shoes and rounded to the nearest centimeter) and body weight (without overcoat and shoes and rounded to kilogram with 1 decimal) will be measured at screening and entered in the eCRF.

#### 7.1.3. Vital Signs

Measurements of heart rate, respiratory rate, temperature, and blood pressure will be performed before and 30 minutes after the end of the IMP infusion on dosing days and at the times specified

in the Schedule of Assessments ([Appendix 3](#)). Temperature must be measured by using the same method on each occasion (e.g., an ear thermometer).

#### **7.1.4. Physical Examinations**

Physical examinations should be performed at screening and as clinically indicated and should include assessment of general appearance, mental status, and various organ systems (neurological, skin, head, eyes, ears, nose, mouth, throat, neck, thyroid, lymph nodes, respiratory, cardiovascular, gastrointestinal, extremities, and musculoskeletal systems).

#### **7.1.5. Neurological Assessments**

Neurological examination will be done according to the National Cancer Institute (NCI) criteria for clinical assessment of nervous system disorders (CTCAE version 5) at the timepoints detailed in the Schedule of Assessments ([Appendix 3](#)). Typical signs and symptoms of medulloblastoma will be entered in the eCRF. Signs and symptoms of medulloblastoma may include headaches, nausea, vomiting, tiredness, dizziness, double vision, poor coordination, unsteady walk, and other concerns. According to RAPNO, any clinical deterioration not attributable to other causes is, by definition, PD. In the absence of clear evidence of PD, it may be assumed that new signs and symptoms are treatment related. Any patient who develops an AE considered to be a Grade 3 or 4 nervous system disorder after the dosimetry infusion will not receive the treatment dose.

#### **7.1.6. Performance Status**

Since most if not all patients will have received prior craniospinal and/or whole-brain irradiation, late side effects for such previous therapies are difficult to distinguish from Lu-DTPA-omburtamab inflicted CNS AEs. However, to evaluate gross changes in neurological function, a performance test (Lansky [<16 years] or Karnofsky [ $\geq$ 16 years]) will be conducted at the Screening, EOT, and all Follow-up Visits in both parts of the trial.

### **7.2. Dosimetry, Pharmacokinetics, Imaging, and Laboratory Evaluations**

#### **7.2.1. Intracerebroventricular Access Device/CSF Flow Assessment**

The patency of the intracerebroventricular access device shunt will be assessed at screening by injecting a small volume (about 0.3 mL) of a radiotracer into the shunt reservoir. The flow of CSF will be measured (for details, see [Appendix 7](#)). Only patients with sufficient flow should be dosed. Efforts to correct CSF flow can be installed and if sufficient flow is established, the patient can be dosed. Abnormal scan findings (ventricular outflow obstruction, obstruction within spinal canal, or failure to ascend to the convexities by 6 hours and spread over the convexities by 24 hours) will result in screening failure and must be documented in the patient's file.

